6.1 Baseline Variable Collection

- Presence or absence of inclusion and exclusion criteria
- Date and time of randomization
- Date of symptom onset
- Admission data: date and time of presentation, origin (home, skilled nursing facility, rehabilitation/LTACH, nursing home, outside hospital, outside ICU), location at enrollment (ED, hospital ward, ICU)
- Demographics (age, sex, race, ethnicity, height, weight)

- Comorbidities: AIDS, Leukemia, Malignant Lymphoma, Hemiplegia, Cerebrovascular Disease, A prior myocardial infarction, Congestive Heart Failure, Peripheral vascular disease, Dementia, COPD, Connective tissue disease, Peptic ulcer disease, History of hypertension, HIV positive (without AIDS), Alcoholism, Coronary artery disease, Rapidly fatal disease, Solid tumor, Liver disease, Diabetes mellitus, Moderate to severe kidney disease
- Acute signs and symptoms: altered mental status, acute hypoxemic respiratory failure, liver function tests, renal function, coagulation studies, chest imaging results
- Sequential Organ Failure Assessment (SOFA)³³ at enrollment
- Chronic use of medication: corticosteroids, ACE inhibitors, angiotensin receptor blockers, non-steroids anti-inflammatory drugs, other
- Receipt of open label antivirals between hospital presentation and enrollment: chloroquine, hydroxychloroquine, remdesivir, lopinavir/ritonavir, other
- Receipt of open label immunomodulators between hospital presentation and enrollment: corticosteroids, tocilizumab, sarilumab, interferon β , other
- Receipt of convalescent plasma between hospital presentation and enrollment
- Receipt of azithromycin between hospital presentation and enrollment
- Receipt of invasive mechanical ventilation, non-invasive ventilation, high-flow nasal cannula, vasopressors, and oxygen therapy at enrollment
- Highest fraction of inspired oxygen, lowest arterial oxygen saturation, highest respiratory rate, lowest systolic blood pressure, highest heart rate in the 12 hours prior to enrollment
- Diagnosis of Acute Respiratory Distress Syndrome (ARDS) by Berlin Criteria³³ at enrollment
- COVID Ordinal Outcomes Scale at enrollment

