- Safety Outcomes: seizure, atrial or ventricular arrhythmia, cardiomyopathy, cardiac arrest, aspartate aminotransferase or alanine aminotransferase levels that are greater than twice the local upper limit of normal, acute pancreatitis (defined by a clinically obtained lipase level above the local upper limit of normal), stage II or greater acute kidney injury according to KDIGO criteria³⁴, receipt of new renal replacement therapy, symptomatic hypoglycemia, neutropenia, lymphopenia, anemia, thrombocytopenia, or severe dermatologic reaction (e.g., Steven's Johnson Syndrome)
- Patient destination at discharge

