3. Ventricular arrhythmia - ventricular tachyarrhythmia (ventricular fibrillation or ventricular tachycardia) treated with a medication or electrical cardioversion or debrillation between randomization and Study Day 29, as documented in the electronic health record or reported by patient or surrogate on follow up telephone call.
4. Cardiac arrest - Between randomization and Study Day 29, as documented in the electronic health record or reported by patient or surrogate on follow up telephone call. Does not include expected cardiac arrests occurring as a part of the dying process for patients on comfort measures.
5. Elevation in aspartate or alanine aminotransferase to twice the upper limit of normal – Between randomization and Study Day 29, as documented in the electronic health record or reported by patient or surrogate on follow up telephone call.
6. Acute Pancreatitis – Clinically-obtained lipase level above the local upper limit of normal between randomization and day 29.
7. Acute Kidney Injury – Stage II or greater acute kidney injury by Kidney Disease Improving Global Outcomes (KDIGO) Criteria between randomization and day 29, defined as any of the following:
 - a. Creatinine at least 2.0 times the baseline value
 - b. Increase in serum creatinine above 4.0 mg/dl
 - c. Urine output less than 0.5 ml/kg/h for at least 12 hours
 - d. Initiation of new renal replacement therapy
8. Receipt of renal replacement therapy – Between randomization and Study Day 29, as documented by treating clinicians in the electronic health record or reported by patient or surrogate on follow up telephone call.
9. Symptomatic hypoglycemia – Between randomization and Study Day 29, as documented by treating clinicians in the electronic health record or reported by patient or surrogate on follow up telephone call.
10. Neutropenia – Clinically-obtained absolute neutrophil count < 1000 (cells/mm³) between randomization and Study Day 29
11. Lymphopenia – Clinically obtained absolute lymphocyte count < 1000 (cells/mm³) between randomization and Study Day 29.
12. Anemia – Clinically-obtained hemoglobin < 12.0 g/dL between randomization and Study Day 29.

13. Thrombocytopenia – Clinically-obtained platelet count < 50 (cell/mm³; in thousands) between randomization and Study Day 29.

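### The SAP's acute kidney injury rule can count advanced chronic kidney disease as acute injury, because limb b sets no minimum creatinine rise and limb c no baseline condition

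*SAP*

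**What the plan says.** SAP Appendix B, Definition of Safety Outcomes, item 7 introduces the outcome as "Stage II or greater acute kidney injury by Kidney Disease Improving Global Outcomes (KDIGO) Criteria between randomization and day 29, defined as any of the" limbs listed beneath it. There are four:

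- Limb a is relative and asks for a creatinine that has at least doubled from baseline.
- Limb b is absolute and is worded "Increase in serum creatinine above 4.0 mg/dl", with nothing further on size or timing.
- Limb c turns to diuresis over half a day and is worded "Urine output less than 0.5 ml/kg/h for at least 12 hours", again with nothing further.
- Limb d covers dialysis, but only where it is newly started.

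The protocol does not write the limbs out. Its section 6.2 asks for "stage II or greater acute kidney injury according to KDIGO criteria" and lists dialysis as a separate item, likewise limited to new therapy.

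None of the 16 exclusion criteria (protocol 3.2, SAP 4.2) concerns kidney function or dialysis. The baseline form in protocol 6.1 expects such patients, since it lists "Moderate to severe kidney disease" as a comorbidity. SAP 7.1 analyses all enrolled patients unless otherwise specified, and SAP 7.5 analyses safety outcomes by logistic regression without covariates. No rule removes patients with prior kidney failure from item 7.

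**The concern.** Limbs a and d describe acute change: a doubling from baseline, or dialysis that is new. Limbs b and c do not, and either one alone creates an event. Limb b accepts an increase of any size, provided it ends above 4.0 mg/dl. Limb c compares nothing with the patient's usual state. A patient whom limb d was worded to leave out, because dialysis began before the trial, can come back in through limb b or c.

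At stake is the readability of one named safety outcome. Events that reflect chronic disease fall in both arms, raise the reported rate of stage II or greater injury, and pull the odds ratio towards 1. For a safety outcome, dilution works against detecting harm.

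**Working it through.** The documents state no event rate, effect size or power for acute kidney injury, so there is no figure of theirs to reproduce. Three checks follow.

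**1. Limb b against limb a.** For baseline creatinine B (mg/dl), limb a needs 2.0 × B. Limb b needs a rise just over 4.0 − B, which is a fold-rise just over 4.0 / B.

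| B | Limb a met at | Limb b: rise must exceed | Limb b: fold-rise must exceed |
|---|---|---|---|
| 2.0 | 4.0 | 2.0 | 2.00 |
| 3.0 | 6.0 | 1.0 | 1.33 |
| 3.5 | 7.0 | 0.5 | 1.14 |
| 3.9 | 7.8 | 0.1 | 1.03 |

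The limbs agree at 2.0 and part company above it. At a baseline of 4.0 or more, any upward move ends above 4.0, so 5.0 to 5.1 qualifies if the phrase means that creatinine rises and is above 4.0.

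The phrase could also mean a rise *of* more than 4.0 mg/dl. Then the value reached exceeds B + 4.0, and B + 4.0 ≥ 2B whenever B ≤ 4.0, so limb a already captures the case. On that reading limb b adds something only for baselines above 4.0. A rise *to* above 4.0 is therefore the more natural reading, but the text does not settle it.

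How often could ordinary variation trigger limb b? Assume no true change, seven independent daily values and a within-patient coefficient of variation of 5% or 8% (none of these is in the documents). The simulated chance of at least one value above 4.0 is:

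| B | CV 5% | CV 8% |
|---|---|---|
| 3.5 | 1% | 23% |
| 3.7 | 31% | 69% |
| 3.9 | 92% | 96% |

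The result depends heavily on how close the baseline is to the cut-off. The share of patients at such baselines is not given.

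**2. Limb c.** The 12-hour threshold is 0.5 × weight × 12: 0.5 × 70 × 12 = 420 mL at 70 kg, 480 mL at 80 kg, 600 mL at 100 kg. A patient producing less than this meets limb c however long that has been so. A dialysis patient with more residual output does not.

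**3. Dilution, as an upper bound.** Let a share c of each arm be on chronic dialysis and let all of them be counted. With true rate p in the rest, the counted rate is q = c + (1 − c) × p. Assume p = 10% and 18%. For c = 2%: q = 0.02 + 0.98 × 0.10 = 0.118 and 0.02 + 0.98 × 0.18 = 0.196, giving an odds ratio of (0.1964/0.8036) / (0.118/0.882) = 1.83.

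| c | Counted rates | Odds ratio | False share of events, lower-rate arm (c/q) | Patients of 510 |
|---|---|---|---|---|
| 0 | 10.0% vs 18.0% | 1.98 | 0% | 0 |
| 2% | 11.8% vs 19.6% | 1.83 | 17% | about 10 |
| 4% | 13.6% vs 21.3% | 1.72 | 29% | about 20 |
| 6% | 15.4% vs 22.9% | 1.63 | 39% | about 31 |

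Dilution is stronger when true rates are lower. At an assumed 5% versus 10%, the odds ratio of 2.11 becomes 1.81 at c = 2% and 1.57 at c = 5%.

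**The case against.** **The heading already restricts the outcome to acute injury.** It invokes KDIGO stage II or greater after randomization, so the intent is clear. But the heading then defines the outcome by the list, and the list is what will be programmed. Elsewhere the SAP writes its carve-outs down: in the ECMO composite, patients already on ECMO at randomization cannot qualify by continuing it, and the cardiac arrest item leaves out expected arrests under comfort care. Item 7 does so only in limb d.

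**A reader might infer that every patient with stable chronic kidney failure is counted.** The text does not support that. Limb b requires an increase, so a creatinine that stays flat at 5.0 does not meet it.

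**A reader might infer that all dialysis patients meet limb c daily.** Only those who are anuric or oliguric and have urine output charted over 12 hours do. SAP Appendix C lists highest creatinine among on-study values but no urine output, so how often limb c would apply is unknown. This is also why the dilution figures are upper bounds.

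**A reader might take protocol 2.1.3 to say that the drug injures the kidney.** It says that the drug's risks may be greater when renal function is already reduced. The risk list in protocol 9.1.1 has no renal item.

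**The consequence is limited.** This stands. Allocation is blinded and 1:1, so misclassification should be similar in both arms. The suggested stopping criteria (SAP 4.3) use the Day 15 ordinal scale, no power is claimed for this outcome, and renal replacement therapy is reported separately as item 8.

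**Conclusion.** The point holds as a defect of definition: as written, item 7 *can* count advanced chronic kidney disease as stage II or greater acute injury, through a trivial creatinine rise under limb b or long-standing low urine output under limb c. Nothing in eligibility, the analysis set or the model corrects for it. The expected effect is an inflated rate and a diluted difference, not a bias favouring one arm.

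The size cannot be fixed from the documents. The fall in odds ratio from 1.98 to between 1.83 and 1.63 rests on assumed true rates of 10% and 18%, an assumed dialysis share of 2% to 6%, and the counting of every such patient. The simulated percentages for limb b apply only to patients just under the cut-off and do not translate into a trial-level figure. This is a minor point about one safety outcome, worth correcting because the correction is cheap.

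**What to change.** In SAP Appendix B, item 7:

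1. Treat patients on chronic renal replacement therapy at randomization as not at risk. Remove them from numerator and denominator and report their number by arm. The status precedes randomization, so the comparison among the remaining patients is still randomized.
2. Define baseline creatinine for limbs a and b. The highest value in the 24 hours before randomization is already recorded for SOFA.
3. Reword limb b as a rise *to* above 4.0 mg/dl together with a stated minimum rise from the enrolment creatinine. The sponsor should choose the size so that it is consistent with the KDIGO criteria the SAP invokes.

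**Cost.** Mostly wording. Chronic dialysis is not a listed baseline variable in protocol 6.1, so one chart-review field may be needed, although limb d and the new-therapy wording of protocol 6.2 already require that knowledge. The same field would let item 8, which omits the word new, be aligned with protocol 6.2.

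**Downside.** The denominator is slightly smaller and the reported rate lower. Some acute-on-chronic cases with a small rise may be lost: purely as illustration, a 1.5-fold minimum would drop a rise from 3.0 to 4.4 mg/dl (4.4/3.0 = 1.47). Limb c remains open to oliguric patients who are not on dialysis.

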5.3 Safety outcomes

- Seizure
- Atrial or ventricular arrhythmia
- Cardiac arrest

- Elevation in aspartate aminotransferase or alanine aminotransferase to twice the local upper limit of normal
- Acute pancreatitis
- Acute kidney injury
- Receipt of renal replacement therapy
- Symptomatic hypoglycemia
- Neutropenia, lymphopenia, anemia, or thrombocytopenia
- Severe dermatologic reaction

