7. DATA ANALYSIS PLAN

7.1 Trial Population

The primary population for analysis will be all patients enrolled in the trial. The primary approach to analysis will be by intention to treat, in which patients assigned to the hydroxychloroquine group are analyzed in the hydroxychloroquine group and patients assigned to the placebo group are analyzed in the placebo group, regardless of treatments received. All analyses will be intention-to-treat analyses among all enrolled patients unless otherwise specified.

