7.5 Analysis of Secondary and Safety Outcomes

Ordinal secondary will be analyzed using a proportional odds model with randomized group assignment as an independent variable and the covariables used in the primary model. Binary secondary outcomes will be analyzed using multivariable logistic regression models with the same pre-specified covariates. Survival and hospital discharge through day 28 will be analyzed using multivariable proportional hazards regression with the same covariates in the primary outcome model. For the hospital discharge model, death will be treated as a competing risk, and the sub-distribution hazard ratio will be reported.⁶ Safety outcomes will be analyzed with simple logistic regression without co-variable adjustment.

Detailed data on receipt of invasive mechanical ventilation, vasopressors, intensive care unit admission, and hospitalization were collected during the index hospitalization, but not after discharge from the index hospitalization. Therefore, the main analysis of the associated “-free day” outcomes will use information regarding receipt of the supportive therapy between randomization and hospital discharge or Study Day 29, whichever occurs first (“in-hospital outcome”). Information on death between discharge from the index hospitalization and Study Day 29 is systematically available via follow-up phone calls. Hence, we will use all-cause, all-location death in the calculation of “-free day” outcomes.

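### SAP safety item 8 counts any renal replacement therapy after randomization, including dialysis already under way at entry, while protocol section 6.2 specifies new therapy only

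*SAP*

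**What the plan says.** Item 8 of the safety definitions in SAP Appendix B reads "Receipt of renal replacement therapy – Between randomization and Study Day 29, as documented by treating clinicians in the electronic health record", and a report by the patient or surrogate at a follow-up call also counts. It has no condition on status at randomization.

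Protocol section 6.2, which lists what is collected in hospital, has "receipt of new renal replacement therapy". The outcome list in protocol section 5.3 has only "Receipt of renal replacement therapy". The protocol's study summary, SAP section 6.3 and SAP Appendix A use the same unrestricted label.

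Item 7d of SAP Appendix B, one component of acute kidney injury, has "Initiation of new renal replacement therapy".

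SAP section 7.1 states "All analyses will be intention-to-treat analyses among all enrolled patients unless otherwise specified", and section 7.5 states "Safety outcomes will be analyzed with simple logistic regression without co-variable adjustment". Nothing in the analysis therefore removes or adjusts for patients already on therapy at entry.

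**The concern.** The two definitions give different counts as soon as one enrolled patient is on dialysis at randomization. Such patients can be enrolled: none of the 16 exclusion criteria in protocol section 3.2 names dialysis or kidney disease, and section 6.1 records moderate to severe kidney disease as a comorbidity.

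A patient on long-term dialysis will almost certainly receive it again before Day 29, whichever arm he or she is in. Under item 8 as written, that patient is a safety event that the study drug cannot have caused. The event rate then overstates new renal failure in both arms, and a real difference is harder to see. In a safety table, a diluted comparison can be mistaken for reassurance.

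The SAP avoids this problem elsewhere. In the composite of death or ECMO, a patient on ECMO at randomization cannot qualify merely by staying on it. Item 8 has no such rule.

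**Working it through.** **Text comparison**

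| Place | Restricted to new therapy? |
|---|---|
| Protocol study summary; protocol 5.3 | No |
| Protocol 6.2 (in-hospital collection) | Yes |
| SAP 6.3; SAP Appendix A | No |
| SAP Appendix B, item 8 (definition) | No |
| SAP Appendix B, item 7d (part of a different outcome) | Yes |

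The conflict lies between the SAP definition and protocol 6.2, and also inside the protocol, between 5.3 and 6.2.

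**Size.** The plan states no event rate or power for any safety outcome, so there is no figure to reproduce. Inputs:

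- From the documents: 510 patients, 1:1 allocation, so n = 255 per arm; unadjusted comparison.
- Assumed: new therapy in p0 = 5% (placebo) versus p1 = 10% (hydroxychloroquine); a share q = 1%, 2% or 5% on dialysis at randomization, equal in both arms, all of whom re-qualify. Two-sided 5% is a yardstick only, since the SAP sets no alpha for safety.

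Formulas:

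- Observed risk under item 8: P = q + (1 − q)p.
- Odds ratio: [P1/(1 − P1)] / [P0/(1 − P0)].
- Power: Φ{(|P1 − P0| − 1.96·√[2P̄(1 − P̄)/n]) / √[(P0(1 − P0) + P1(1 − P1))/n]}, where P̄ is the mean of P0 and P1.
- New therapy only: the same power formula with p0, p1 and n = 255(1 − q).
- Share of placebo events already present at entry: q/P0.

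Worked case, q = 2%:

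- P0 = 0.02 + 0.98 × 0.05 = 0.069; P1 = 0.02 + 0.98 × 0.10 = 0.118.
- Odds ratio = (0.118/0.882)/(0.069/0.931) = 1.81.
- P̄ = 0.0935. Numerator of the power term: 0.0490 − 1.96 × 0.02578 = −0.0015. Denominator: 0.0257. Φ(−0.06) = 48%.
- Pre-existing share of placebo events = 0.02/0.069 = 29%.

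| On dialysis at entry | Observed OR, item 8 as written | Power, as written | Power, new therapy only | Placebo events pre-existing |
|---|---|---|---|---|
| 0% | 2.11 | 57% | 57% | 0% |
| 1% | 1.93 | 52% | 57% | 17% |
| 2% | 1.81 | 48% | 56% | 29% |
| 5% | 1.57 | 38% | 55% | 51% |

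With rarer events (3% versus 6%, OR 2.06), power as written is 31%, 27%, 20% at q = 1%, 2%, 5%, against 37%, 37%, 36% for new therapy only.

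The denominator is immaterial. At q = 2%, power for new therapy is 56% whether patients on dialysis at entry are dropped or kept as non-events.

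A simulation of 100,000 trials per scenario, with a Wald test on the unadjusted log odds ratio, agrees for 5% versus 10%: 47.5% against 56.2% at q = 2%, and 37.2% against 54.3% at q = 5%.

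**The case against.** The strongest reply is that this is a slip of wording with no demonstrated effect. Item 8 agrees with the protocol's own outcome lists, and protocol 6.2 suggests that the in-hospital field already asks for new therapy. If it does, the in-hospital count is right. That stands, and it is why the point is minor. It does not make the item safe as written: the SAP definition is what a programmer follows, and item 8 also accepts telephone reports after discharge, which the wording of 6.2 does not cover.

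Item 7d defines acute kidney injury, not this outcome. That also stands: it shows inconsistent use of the word new, not a second definition of item 8.

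Two stronger readings are tempting, and the documents support neither.

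- *A reader might infer bias between arms.* Allocation is randomized and blinded, so pre-existing dialysis balances in expectation. The effect is dilution.
- *A reader might infer that the other safety items are wrong for the same reason*, for example "Elevation in aspartate or alanine aminotransferase to twice the upper limit of normal" or "Clinically-obtained hemoglobin < 12.0 g/dL between randomization and Study Day 29". Protocol 6.2 sets no new-onset condition for these, so nothing is contradicted. Baseline platelets are recorded for the SOFA score, but protocol 6.1 lists liver function tests without naming AST or ALT. SAP Appendix C already compares highest AST and ALT and lowest hemoglobin and platelets by arm. Nor is a new-onset row clearly better. Assume new transaminase elevation in 10% versus 20%, with 70% of pre-existing cases re-qualifying and 70% of patients having a baseline value. The all-patient row then has power 80%, 71%, 40% at prevalence 5%, 10%, 30%, against 73%, 71%, 60% for the new-onset row: a loss, a tie, and a gain only at the highest prevalence, which no document supports.

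**Conclusion.** The point holds for item 8 and is minor. As written, item 8 would record continuing dialysis as a drug-safety event, contrary to protocol 6.2 and unlike the SAP's own rule for ECMO.

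Under the assumed 5% versus 10%, the loss of power is about 5, 9 and 18 percentage points at 1%, 2% and 5% on dialysis at entry (from unrounded values). The size rests wholly on assumed rates, on equal prevalence in both arms, and on every patient on dialysis at entry re-qualifying. It is nil if nobody was on dialysis at randomization or if the data record only new therapy.

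A separate wording point concerns follow-up. SAP Appendix B describes all safety outcomes as assessed to Day 29 regardless of location, and item 5 (transaminases) accepts telephone reports. Protocol section 6.3.1 collects only non-laboratory safety outcomes after discharge. These passages should be reconciled.

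**What to change.** 1. Redefine item 8 as renal replacement therapy newly started after randomization and up to Day 29, and state that a patient on it at randomization does not qualify by continuing it. Apply the same rule to telephone reports.
2. Align the labels in the protocol study summary, protocol 5.3, SAP 6.3 and SAP Appendix A with protocol 6.2.
3. Reconcile the all-location description and the telephone wording of item 5 with protocol 6.3.1.

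New-onset rows for transaminases and platelets may be added beside the existing rows as optional supplements. They are not corrections.

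Cost: wording changes in the SAP and also in the protocol. If the data do not already separate new therapy, dialysis status at randomization must be established from the chart or the comorbidity record, because renal replacement therapy is not among the supports that protocol 6.1 records at enrollment. The primary analysis is unaffected, and no new patient contact is needed.
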